7.7.4 Titration Skin test

End point titration SPT will be conducted by a study nurse using commercial peanut test extract (Greer) at full strength and four 10-fold serial dilutions in saline prepared by the study nurse or pharmacy on the day of use and stored at 4°C. Histamine and saline controls will be administered at the same time and the mean orthogonal diameters of the wheal will be measured for each test by the study nurse after 15 minutes.

7.7.5 Symptom Assessment

Symptoms will be recorded by participants using a 2 week diary and reviewed at each visit by the research coordinator and study physician (see Appendix 16.2).

7.7.6 Phlebotomy

At visits 0, 27 and 30, 3ml/kg (for participants <18 years and/or participants weighing <50 kg) or 1 unit (550 ml) of blood will be obtained by standard venipuncture at the MGH blood bank. One (1) ml of blood will be used to measure peanut specific IgE, IgG, and IgG4. Five (5) ml of blood will be used to measure basophil activation. The remaining blood will be used for mechanistic T cell and B cell studies. Prior to each scheduled large blood draw, a rapid test of hemoglobin level will be performed.

The following criteria will be used to determine for adult participants whether the proposed 550 ml can be drawn:

- AGE must be at least 18 years old
- WEIGHT must be greater than 110 lbs (50 kg);
- PULSE must be between 50 and 100 beats/minute with no cardiac irregularity;
- TEMPERATURE must not exceed 37.55°C or 99.5°F;
- Hematocrit < 0.36 for adult females or < 0.38 for adult males;

An additional blood collection of \leq 200 ml (adults) and 3ml/kg (children) will occur after 12 weeks of treatment to be used for mechanistic B cell studies. For B cell studies, 100-200 million PBMCs will be used for affinity single-cell sorting of Arah2-specific B cells by flowcytometry (see Patil et al. 2015 JACI) as well as bulk sorting of CD19+ CD27+ IgM- cells. These will be used for cloning of functional mAbs and next generation sequencing of BCR, respectively.

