Exclusion Criteria	 History of severe anaphylaxis Severe or Moderate asthma Poorly controlled asthma Diagnosis of other severe or complicating medical problems, including autoimmune or chronic immune inflammatory conditions or gastrointestinal inflammatory conditions Inability to cooperate with and/or perform oral food challenge procedures Primary Immune Deficiency Allergy to oat confirmed by skin prick testing and history Current use of beta blockers, angiotensin converting enzyme inhibitors, or monoamine oxidase inhibitors Women of childbearing potential who are pregnant, planning to become pregnant, or breastfeeding Use within the past 6 months of other systemic immunomodulatory treatments Hematocrit <0.36 for adult females or <0.38 for adult males Weight <23 kg
Investigational Product / Intervention	Active peanut flour vs. placebo oat flour
Study Procedures	OIT, DBPCFCs, physical examination, pregnancy testing, phlebotomy, PFTs
Statistical Considerations	n=40, 3:1 active to placebo; Per protocol analysis of the Treg proportion by clinical outcome for the anticipated 22 subjects completing DBPCFC3; effect size of 1.5 for primary outcome [?]; 27% (n=8) combined Partial Tolerance / Tolerance versus Treatment Failure (n=14).

Contents

1	BAC	CKGROUND AND RATIONALE	12
	1.1	Background	12
	1.2	Rationale for Selection of Study Population	12
	1.3	Investigational Product(s) / Intervention(s)	12
	1.4	Rationale for Selection of Investigational Product(s) / Intervention(s) and Regimen	13
	1.5	Preclinical and Clinical Experience	13
		1.5.1 Preclinical Studies	13
		1.5.2 Clinical Studies	14
	1.6	Risks	14
		1.6.1 Risks of Investigational Product(s) / Intervention(s)	14
		1.6.2 Risk of Study Procedures	14
		1.6.2.1 Double-blind placebo controlled food challenge (DBPCFC)	14
		1.6.2.2 Desensitization Procedure	15
		1.6.2.3 Allergy Prick Skin Testing	15
		1.6.2.4 Blood Draw	15
		1.6.3 Risk of Concomitant Medications, Prophylactic Medications and Rescue Medications	15
	1.7	Benefits	16
	• • •	1.7.1 Benefits of Investigational Product(s) / Intervention(s)	16
		1.7.2 Benefits of Study Procedure(s)	16
		1.7.2 Deficites of Study Frocedure(s)	10
2	OBJ	IECTIVES	16
	2.1	Primary Objective(s)	16
	2.2	Secondary Objective(s)	16
		2.2.1 Clinical:	16
		2.2.2 Mechanistic:	17
		2.2.3 Exploratory:	17
			• •
3	STU	DY DESIGN	17
	3.1	Study Endpoints	18
		3.1.1 Primary Endpoint(s)	18
		3.1.2 Secondary Endpoint(s)	18
	3.2	Study Completion	19
4	SEL	ECTION AND WITHDRAWAL OF PARTICIPANTS	19

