- **1.6.2.4 Blood Draw** May aggravate a pre-existing anemic condition but this risk is negligible since the volume of blood to be drawn at each visit will be at most 3 ml/kg in pediatric participants and 1 unit of blood in adult participants. Blood draws will occur four times spread out over the 90 week study (See Section 7 for specific schedule). Other risks are those related to any needle puncture, including slight bruising, local infection, or the possibility of the participant fainting. The discomfort involved is minimal.

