4.2 Exclusion Criteria

Individuals who meet any of these criteria are not eligible for enrollment as study participants:

- History of severe anaphylaxis as defined by hypoxia (cyanosis or SpO2 <92% during reaction), documented
 hypotension (documented systolic BP >30% below predicted normal for sex, height, weight or from known
 baseline), neurological compromise (confusion, loss of consciousness), or incontinence.
- Severe or Moderate asthma as defined using the severity criteria of the current NHBLI Guidelines for the Diagnosis and Management of Asthma (http://www.nhlbi.nih.gov/guidelines/asthma/).

- Poorly-controlled asthma as defined by FEV1 <80% or any of the following symptoms: nighttime awakening >2 days/week or rescue medication use >2 days / week.
- Diagnosis of other severe or complicating medical problems, including autoimmune or chronic immune inflammatory conditions or gastrointestinal inflammatory conditions, including Celiac Disease, Inflammatory Bowel Disease and Eosinophilic Gastrointestinal Disorders
- Inability to cooperate with and/or perform oral food challenge procedures.
- Primary Immune Deficiency
- Allergy to oat confirmed by skin prick testing and history
- Current use of beta blockers, angiotensin converting enzyme inhibitors, or monoamine oxidase inhibitors
- Women of childbearing potential who are pregnant, planning to become pregnant, or breastfeeding
- Hematocrit < 0.36 for adult females or < 0.38 for adult males
- Weight <23 kg
- Use within the past 6 months of other systemic immunomodulatory treatments including allergen immunotherapy, or use of biologics with an immune target, including omalizumab.
- Past or current medical problems or findings from physical examination or laboratory testing that are not listed above, which, in the opinion of the investigator, may pose additional risks from participation in the study, may interfere with the participant's ability to comply with study requirements or that may impact the quality or interpretation of the data obtained from the study may also exclude a participant from the study.

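### Section 7.7.6 states the hematocrit condition for the 550 ml draw the wrong way round: read literally, it clears adults with low hematocrit and bars those with adequate values

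*Combined protocol and SAP*

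**What the plan says.** Section 7.7.6 sets the large research draws: "At visits 0, 27 and 30, 3ml/kg (for participants <18 years and/or participants weighing <50 kg) or 1 unit (550 ml) of blood". It introduces the adult safety list with "The following criteria will be used to determine for adult participants whether the proposed 550 ml can be drawn". Four items follow as requirements, beginning with "AGE must be at least 18 years old" and continuing with weight, pulse and temperature. The fifth item has no verb: "Hematocrit < 0.36 for adult females or < 0.38 for adult males".

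The synopsis carries the same line among its exclusions, "Hematocrit <0.36 for adult females or <0.38 for adult males", and Section 4.2 repeats it with the same sign and cut-offs under the lead-in "Individuals who meet any of these criteria are not eligible for enrollment as study participants".

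Two other statements bear on anemia. Section 7.7.6 says "Prior to each scheduled large blood draw, a rapid test of hemoglobin level will be performed" but gives no limit for the result. Section 1.6.2.4 says of the blood draw "May aggravate a pre-existing anemic condition but this risk is negligible since the volume of blood to be drawn at each visit".

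**The concern.** The same inequality serves as a bar to enrollment in Section 4.2 and stands among conditions for going ahead in Section 7.7.6. It cannot be right in both places. If the last item in 7.7.6 is read as the four before it are, the threshold is inverted.

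What is at stake is the safety of adults giving a full unit, chiefly at the second and third large draws. Section 4.2 is applied at entry. Visit 27 falls in maintenance and visit 30 in avoidance, roughly a year or more after baseline, and an adult enrolled with an adequate value may have dropped below the limit by then. The rule meant to catch that person is the one written backwards.

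**Working it through.** No figure in the plan needs reproducing. The check sets the texts side by side, tests the rule on example values, and then sizes the draw that the line controls.

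**1. Direction of each item in the 7.7.6 list**

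| Item | Requirement | Meeting it means |
|---|---|---|
| Age | 18 years or more | draw may proceed |
| Weight | above 50 kg | draw may proceed |
| Pulse | 50 to 100, regular | draw may proceed |
| Temperature | not above the stated limit | draw may proceed |
| Hematocrit | below 0.36 (F) or 0.38 (M) | draw may proceed, if read in parallel |

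In Section 4.2, meeting the same hematocrit line makes the person ineligible.

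**2. Rule applied to example values**

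| Adult | Hematocrit | Section 4.2 at entry | 7.7.6 as written | 7.7.6 with sign reversed |
|---|---|---|---|---|
| Female | 0.33 | excluded | draw permitted | draw barred |
| Female | 0.40 | not excluded | draw barred | draw permitted |
| Male | 0.35 | excluded | draw permitted | draw barred |
| Male | 0.44 | not excluded | draw barred | draw permitted |

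As written, the two sections contradict each other. No adult who satisfies 4.2 could give 550 ml at the first large draw. At visits 27 and 30, only adults whose hematocrit had since fallen below the limit would qualify. With the sign reversed, the two sections agree in every row.

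**3. Does any other text correct the line?**

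- Section 4.2 applies to enrollment only. The Schedule of Events places visit 27 within Days 350–434 and the avoidance visits within Days 434–518.
- The rapid hemoglobin test has no cut-off.
- The withdrawal criteria (4.3) and the individual stopping rules (8.1.2) contain no anemia limit.
- The Schedule of Events lists no hematocrit measurement.

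So at visits 27 and 30 the 7.7.6 line is the only numeric anemia limit.

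**4. Size of the draw the line controls**

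Total over three draws: 3 × 550 = 1,650 ml. The weights below are illustrative; 50 kg is the lower boundary of the list's weight condition.

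| Weight | 550 ml per kg | Volume at 3 ml/kg | Ratio |
|---|---|---|---|
| 50 kg | 550/50 = 11.0 ml/kg | 150 ml | 550/150 = 3.7 |
| 70 kg | 550/70 = 7.9 ml/kg | 210 ml | 550/210 = 2.6 |
| 100 kg | 550/100 = 5.5 ml/kg | 300 ml | 550/300 = 1.8 |

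The line does not govern the additional B-cell draw of at most 200 ml in adults. Nor does it apply to participants under 18 or under 50 kg, who give 3 ml/kg.

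**The case against.** The best reply is that the line is ambiguous rather than inverted. The lead-in to the list is neutral about direction, and the hematocrit item has no verb, so the inverted meaning comes from its neighbours. The inverted reading also defeats itself: it would stop every eligible adult from giving the full unit at baseline, so staff would notice at once and find the intended direction in 4.2. For a low-hematocrit adult to be drawn, someone would have to read the line backwards and also disregard a low hemoglobin result. Visits include a history and examination, and the investigator may withdraw a participant for added medical risk.

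Much of this stands as an argument about practical risk. Blood-bank staff would probably infer the intent, and no actual harm is claimed. It does not remove the error. Even on the neutral reading, the list changes direction at its last item without saying so. The other protections are discretionary and carry no number.

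Two narrower points are also fair. The ml/kg ratios describe the volume at issue, not the number of people affected; the documents give neither the number of adults nor how many might fall below the limit, and do not say that an adult failing the item would move to 3 ml/kg. And the pre-draw test measures hemoglobin while the cut-off is in hematocrit. Neither point alters the need to correct the line.

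**Conclusion.** The concern holds. The hematocrit item in 7.7.6 is wrong as written: read in parallel with the rest of its list it permits the draw in the people it should protect, and it contradicts 4.2. The conclusion rests on that parallel reading, and on 4.2 and the anemia risk named in 1.6.2.4 as evidence of intent. Its reach is limited to adults over 50 kg at the three 550 ml draws, with the practical exposure at visits 27 and 30, where no other numeric limit applies. The likelihood of harm is low because the intent can be inferred, but a safety threshold should not depend on staff recognising that it is reversed. The estimand, power and planned analysis are not affected. It should be fixed.

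**What to change.** Replace the last item of the list in Section 7.7.6 with: HEMATOCRIT must be at least 0.36 for adult females or at least 0.38 for adult males. Leave Section 4.2 and the synopsis unchanged, since the inequality is correct there.

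The change is one line, with no effect on sample size, visit schedule or analysis. In the same edit the sponsor could usefully state how hematocrit is to be obtained before the later draws, or give the rapid hemoglobin test its own limit. That addition is optional, and the correction does not depend on it.

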4 SELECTION AND WITHDRAWAL OF PARTICIPANTS

4.1 Inclusion Criteria

Individuals who meet all of the following criteria are eligible for enrollment as study participants:

- Diagnosis of peanut allergy by medical history
- Evidence of peanut-specific IgE by either: positive skin prick test to peanut (reaction wheal at least 5 mm larger than saline control) or serum peanut-specific IgE ≥5 kU/L at screening visit.
- Ara h 2 specific IgE >0.35 kU/L at screening visit.
- Who are willing to sign informed consent or whose parent or legal guardian is willing to sign the consent form (age appropriate)
- Who are willing to sign the assent form, if age appropriate
- Males and females of all ethnic/racial groups aged 7-55 years old who are otherwise healthy.
- React to ≤443 mg of peanut protein during DBPCFC1

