7.4.4 Maintenance Visits (Days 350-434)

Maintenance visits will occur on the MGH CRC monthly during the 12 weeks of maintenance therapy. Each visit will involve a medical history and physical examination. The medical history will consist of a structured interval clinical history and review of systems concerning any types of allergic symptoms related to their food allergy, atopic dermatitis or asthma. The participants and/or their parents will record any known accidental ingestion that occurs during the study. The physical exam will include vital signs, and spirometry. A negative urine pregnancy test will be documented for female participants of child-bearing potential; if the test is positive, the visit will be cancelled and if pregnancy is confirmed, the subject will be withdrawn from the study.

Blood will be collected and skin prick testing will be performed at three follow-up visits for research laboratory studies at baseline, on maintenance therapy (after 12 weeks at 4000 mg of peanut protein or maximum tolerated) prior to DBPCFC2, and prior to DBPCFC3 (12 weeks post avoidance). An additional blood draw will occur during build up (12 weeks after beginning treatment). Blood will be drawn by trained study staff or Clinical Research nurses. Urine will be collected from female participants for a Human Chorionic Gonadotropin (HCG)-based pregnancy test at all follow up visits throughout the study.

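### The week-12 B-cell draw has no weight limit for adults, so an adult under 50 kg may give more blood there than at any of the three main draws

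*Combined protocol and SAP*

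**What the plan says.** For the large draws at visits 0, 27 and 30, section 7.7.6 states: "3ml/kg (for participants <18 years and/or participants weighing <50 kg) or 1 unit (550 ml) of blood will be obtained". Low body weight therefore triggers the lower volume at any age. The same section lists conditions an adult must meet before 550 ml is taken, among them "WEIGHT must be greater than 110 lbs (50 kg" in brackets.

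The additional draw is mentioned in section 7.4.4 without a volume ("An additional blood draw will occur during build up (12 weeks after beginning treatment"). Section 7.7.6 gives its volume as "200 ml (adults) and 3ml/kg (children) will occur after 12 weeks of treatment", with a less-than-or-equal sign before the 200 ml. Nothing there refers to the weight of an adult.

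The general statement in section 1.6.2.4 covers all four draws and also divides by age only: "at most 3 ml/kg in pediatric participants and 1 unit of blood in adult participants" at each visit.

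On eligibility, section 4.1 admits "Males and females of all ethnic/racial groups aged 7-55 years old who are otherwise healthy". The one weight exclusion in section 4.2 is below 23 kg.

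**The concern.** Section 7.7.6 treats 50 kg as the weight below which an adult is to be bled like a child, by the kilogram. It then drops that threshold for the week-12 draw and gives no reason. For a light adult, a supplementary collection may therefore take more than each of the main collections.

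Age alone then separates people of the same size. A 17-year-old and an 18-year-old who both weigh 45 kg have the same limit at visits 0, 27 and 30 but different limits at week 12.

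What is at stake is a small matter of participant safety and internal consistency. The primary endpoint compares baseline with the end of maintenance, so the week-12 sample plays no part in it, in the sample size or in the primary analysis.

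**Working it through.** The plan gives no figure to reproduce here, so the check compares the two limits directly.

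**Inputs**
- Main draws (7.7.6): 3 ml/kg if under 18 and/or under 50 kg, otherwise 550 ml.
- Week-12 draw (7.7.6): at most 200 ml for adults, 3 ml/kg for children.
- Lowest eligible weight (4.2): 23 kg.
- Example weights of 49, 45 and 40 kg are assumptions. The documents give no weight distribution.

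**Where the two limits meet.** 200 / 3 = 66.7 kg. Below that weight, 200 ml is more than 3 ml/kg. At 50 kg the 3 ml/kg limit is 3 × 50 = 150 ml, and 200 / 150 = 1.33. So for every adult under 50 kg the week-12 ceiling is more than 50 ml, and more than 33%, above the main-draw limit.

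**Examples**

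| Adult weight | 3 ml/kg limit | Week-12 ceiling | Ceiling per kg | Excess |
|---|---|---|---|---|
| 49 kg | 3 × 49 = 147 ml | 200 ml | 200/49 = 4.1 ml/kg | 53 ml (200/147 = 1.36) |
| 45 kg | 3 × 45 = 135 ml | 200 ml | 200/45 = 4.4 ml/kg | 65 ml (200/135 = 1.48) |
| 40 kg | 3 × 40 = 120 ml | 200 ml | 200/40 = 5.0 ml/kg | 80 ml (200/120 = 1.67) |

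**Whole study at 45 kg.** Adult: 3 × 135 + 200 = 605 ml. Participant aged 17: 4 × 135 = 540 ml. The ratio is 605 / 540 = 1.12, a difference of 65 ml.

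**Scale.** Just above 50 kg the plan accepts a full unit, 550 / 50 = 11.0 ml/kg. The largest per-kilogram figure in the table is less than half of that.

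**Does another section close the gap?** Section 1.6.2.4 has no weight condition. The weight, pulse, temperature and hematocrit criteria in 7.7.6 are written for the 550 ml collection. The hemoglobin check ("Prior to each scheduled large blood draw, a rapid test of hemoglobin level will be performed") does not say whether week 12 counts as a large draw, and it sets no volume by weight. Section 7.4.4 gives no volume. None of these extends the 50 kg rule to week 12.

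**The case against.** The best defence is that the 50 kg rule is a gate for giving a full unit. Section 7.7.6 offers 3 ml/kg as the alternative to 550 ml and never presents it as a general ceiling for light adults. The week-12 collection is separate, at most 200/550 = 36% of a unit, with its own cap. Its split by age matches section 1.6.2.4, so no limit stated for all draws is broken. Staff may also take 3 ml/kg from a light adult and comply with every sentence.

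The clinical effect is slight too. The draws are spread over more than a year, an adult just over 50 kg may give 3 × 550 + 200 = 1850 ml in total, low hematocrit excludes adults at entry, and the affected group may be empty.

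All of this stands as fact, and it keeps the point minor. It does not explain why the smaller, supplementary draw should allow more from a light adult than each main draw at which the same section holds that person to 3 ml/kg. No passage says the difference is intended. The 200 ml ceiling is also the only volume limit specific to this draw for adults, and it can be reached without a deviation.

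**Conclusion.** The concern holds as a minor inconsistency between draws. Any adult under 50 kg may give over 50 ml (over 33%) more at week 12 than the 3 ml/kg allowed at visits 0, 27 and 30. At 40 to 49 kg the excess is 53 to 80 ml.

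The percentages measure distance from the plan's own limit for the other draws. They do not show that a safety threshold is crossed. The conclusion rests on reading the week-12 sentence literally and on such adults being eligible, which sections 4.1 and 4.2 support. How many will enrol is unknown and could be zero.

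**What to change.** In section 7.7.6, reword the week-12 limit as: 3 ml/kg for participants under 18 years and/or weighing under 50 kg; otherwise up to 200 ml. The same weight condition could optionally be added to section 1.6.2.4 so that the risk statement agrees.

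The cost is one sentence, plus fewer B cells from any adult under 50 kg. At 40 to 49 kg such an adult would still give 120 to 147 ml. For the same draw the plan already accepts 3 × 23 = 69 ml from the lightest eligible child.

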7.7.7 Stool Collection (Optional)

At visits 1, 8, 14, 20, 27, 38 and 50 a stool samples will be collected from the participants up to every three months during the first year, and every 6-12 months once they have reached a maintenance dose. These samples will be banked in an -80F freezer. The stool samples will be used for 16S rRNA sequencing for gut microbiome.

7.7.8 Physical Examination

This will include measurement of heart rate, blood pressure and examination of the skin, ears, nose and throat, lungs and heart.

7.7.9 Urine Pregnancy Testing

For participants of childbearing potential a urine beta-HCG determination will be preformed immediately before each study visit.

7.8 Study Arm Assignment Procedures

7.8.1 Blinding and Randomization

Participants will be randomly assigned to treatment or placebo groups for the first weeks at a ratio of 3:1, after which time, placebo participants will be offered open-label active treatment. Randomization will be performed by the study statistician who will provide that information directly to the CRC dietitian in sealed disclosure envelopes.

